4.1.3 Analysis Populations

The analysis population in this study is defined as the follows

Population	Definition / Criteria	Analyses Evaluated
Safety	
• Comprise of all subjects who receive at least one dose of study product.• This population will be based on the product the subject actually received.	
• Tolerability and Safety

Exclusion of any subjects from the safety population will be reviewed during a BDRM prior to database lock and approved prior to unblinding. PPD will display all randomised subjects included and excluded from the safety population.

4.2 Subject Demographics and Other Baseline Characteristics

Demographic and baseline characteristics summaries will be produced for the Safety Population and the listing will be produced on all randomized subjects.

4.2.1 Demographic Characteristics

Descriptive statistics (number of subjects (n), mean, standard deviation (SD), median, minimum and maximum) for continuous variables and frequency count (n) and percentage (%) of subjects for categorical variables will be presented for demographic variables by product group and overall. Continuous variable will include age (in years) and categorical variables include gender and race. All demographic information will be tabulated in PPD and listed in PPD .

4.2.2 General Medical History

Medical history data will be listed (PPD [redacted]) with start date and end date (or ongoing at the start of study product). A data listing will also be produced for the evaluation of protocol violations at the BDRM.

4.2.3 Characteristics of Disease

Fitzpatrick skin type and the baseline data of primary and secondary variables will be summarised by the number and percentage of subjects (by product group and overall) in PPD [redacted] and listed in PPD [redacted].

4.3 Treatments (Study Product, Rescue Medication, other Concomitant Therapies, Compliance)

4.3.1 Study Product Compliance and Exposure

Compliance data (based on the subject diary data) will also be summarized for the Safety Population as the percentage of subjects in each study product group who took 80% ~ 120% of the number of prescribed uses of study product group (PPD [redacted]).

The compliance (%) will be calculated as [actual number of product use / expected number of product use × 100],

Where,

Expected number of product use = 2 × number of days between the two visits;

Actual number of product use = expected number of product use – missed product use + additional product use.

Study product compliance will be listed (PPD [redacted]). Supervised product application (subject number, date of visit and time of the supervised procedure) will be listed (PPD [redacted]).

The randomization information will be listed in PPD [redacted]. Kit list allocation will be listed in PPD [redacted].

4.3.2 Prior and Concomitant Medication

Prior or concomitant medication taken by or administered to a subject will be recorded in the case report form. The prior and concomitant medications will be coded using an internal validated medication dictionary, GSKDrug.

As justified within Section 5, the current analysis standards for defining concomitant medications will be used rather than those provided in the protocol (which defined concomitant based on the timing of providing informed consent):

- Prior medications are defined as those which stopped before the first application of the study product.

- Concomitant medications are defined as the medication ongoing or started on or after the first application of the study product.

Prior and concomitant medication will be listed (PPD [redacted] and PPD [redacted]) by subject, with drug name, GSK drug synonym, dose, dose form, frequency, route, start date/ study day relative to first study product administration, and ongoing or end date/ study day relative to first study product administration.

Unknown dates will not be imputed, however, if the start or stop date is unknown, then it will be assumed to be a concomitant medication (unless a partial start date / stop date indicates otherwise).

4.4 Analysis of Tolerability

4.4.1 Primary Tolerability Endpoint

4.4.1.1 Primary Tolerability Endpoint Definition

The primary endpoint will be the change from baseline (prior to any product application) in dermatologist signs and symptoms of cutaneous irritation total score following 21 (+2) days of product use.

This study will be considered a success if at least 90% of completed subjects do not have a significant increase (i.e. a unit increase score of 1 in the total score) from baseline in dermatologist assessed signs and symptoms of cutaneous irritation following 21 (+2) days of investigational product use.

Calculation of dermatologist assessment of signs and symptoms of cutaneous irritation total score and change from baseline in total score:

The cutaneous irritation total score will be calculated in the following way:

Cutaneous irritation total score = dermal response score of erythema + dermal response score of dryness + dermal response score of scaling + dermal response score of edema

Where, the dermal response score is described in [Table 4-1](#).

Table 4-1 Dermatological Evaluation

Attribute	Description (Score)				
Erythema	None (0)	Very Slight (0.5)	Slight (1)	Moderate (2)	Severe (3)
Dryness	None (0)	Very Slight (0.5)	Slight (1)	Moderate (2)	Severe (3)
Scaling	None (0)	Very Slight (0.5)	Slight (1)	Moderate (2)	Severe (3)
Edema	None (0)	Very Slight (0.5)	Slight (1)	Moderate (2)	Severe (3)

For example, if the dermal responses score of erythema = 2, dermal responses score of dryness = 0.5, dermal responses score of scaling = 1 and dermal responses score of edema = 0.5.

Then the cutaneous irritation total score will be:

$$\text{Total score} = 2 + 0.5 + 1 + 0.5 = 4.$$

Change from baseline in dermatologist signs and symptoms of cutaneous irritation total score = total score at day 21 – total score at baseline.

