12 STATISTICAL CONSIDERATIONS AND DATA ANALYSES

12.1 Sample Size Determination

A sufficient number of subjects will be screened (approximately 180) to randomize 90 subjects to ensure that at least 60 subjects (30 per arm) complete the study. It is deemed that 30 subjects per arm are considered sufficient to assess the primary endpoint of the dermatologist assessment of signs and symptoms of cutaneous irritation total score. The sample size for this study has been selected based on clinical considerations and to ensure compliance with the ANVISA Guideline for the Safety Evaluation of Cosmetic Products which mandates an investigational product be tested on at least 30 subjects.

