1.4 Sample Size Calculation

A sufficient number of subjects will be screened (approximately 180) to randomize 90 subjects to ensure that at least 60 subjects (30 per arm) complete the study. It is deemed that 30 subjects per arm are considered sufficient to assess the primary endpoint: dermatologist assessment of

signs and symptoms of cutaneous irritation total score. The sample size for this study has been selected based on clinical considerations and to ensure compliance with the Agência Nacional de Vigilância Sanitária (ANVISA) Guideline for the Safety Evaluation of Cosmetic Products (ANVISA, 2012) which mandates an investigational product be tested on at least 30 subjects.

2 Planned Analyses

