4.4.1.2 Statistical Hypothesis, Model, and Method of Analysis

The dermatologist signs and symptoms of cutaneous irritation total score will be calculated as the sum of the individual dermal response attributes (erythema, dryness, scaling, and edema). The change from baseline in the total score will be summarised by number and percentage of subjects by visit for each product group (PPD [redacted]). Additionally the change from baseline score greater than 1 will be summarised by number and percentage of subjects by visit for each product group. No formal statistical inference will be performed.

The individual attribute responses, total score and change from baseline in total score will be listed for each subject by visit and by product group (PPD [redacted]).

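### Success is declared on an observed proportion of at least 90% with no planned measure of precision; at the minimum of 30 completers a bare pass (27/30) has an exact 95% CI of 73.5% to 97.9%

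*SAP*

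**What the plan says.** SAP section 4.4.1.1 states the criterion: "This study will be considered a success if at least 90% of completed subjects do not have a significant increase". A significant increase is explained as "i.e. a unit increase score of 1 in the total score", and the criterion refers to the investigational product after 21 (+2) days. Protocol section 3 has the same rule.

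SAP section 4.4.1.2 summarises the change in total score by counts and percentages for each product and adds a count of changes above 1. It then says "No formal statistical inference will be performed". Protocol section 12.2.6 agrees and names the Safety population as the analysis set.

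On size, Protocol section 12.1 says "It is deemed that 30 subjects per arm are considered sufficient to assess the primary endpoint". SAP section 1.4 plans "to randomize 90 subjects to ensure that at least 60 subjects (30 per arm) complete the study". It gives the basis as follows: "The sample size for this study has been selected based on clinical considerations and to ensure compliance with the" ANVISA guideline, "which mandates an investigational product be tested on at least 30 subjects". Neither document gives an expected rate, confidence level, power or interval.

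**The concern.** The plan does more than describe a sample. It calls the study a success or not by comparing one proportion with a fixed threshold, and Protocol section 2.1 wants the data to show a favourable tolerance profile before commercialisation. That is a statement about future users. With about 30 subjects, an observed 90% is compatible with a wide range of true rates, and a report that says only that the target was met does not convey this. The documents call 30 per arm sufficient without showing what a 90% rule can distinguish at that number.

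**Working it through.** **Inputs.** Threshold: at least 90% of completers without a significant increase (SAP 4.4.1.1). Completers: at least 30 per arm, from 90 randomized (SAP 1.4). Not stated, so assumed here: 1:1 allocation, giving 90/2 = 45 per arm at most; and the confidence level, shown as two-sided 95% and one-sided 95%.

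**The plan's own figure.** There is no statistical calculation to reproduce. Going from 90 randomized to 60 completers implies a loss of 1 − 60/90 = one third, and 60/(1 − 1/3) = 90. No dropout rate is stated.

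**Step 1: what passes.** The smallest passing count is 0.9n rounded up. For n = 30 this is 27. For n = 45, 0.9 × 45 = 40.5, so 41.

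**Step 2: exact limits.** For x subjects without an increase out of n, the Clopper-Pearson lower limit is the *a* quantile of Beta(x, n − x + 1), with *a* = 0.025 (two-sided 95%) or 0.05 (one-sided 95%). The two-sided upper limit is the 0.975 quantile of Beta(x + 1, n − x). When x = n the lower limit reduces to *a*^(1/n): for 30/30, 0.025^(1/30) = 88.4% and 0.05^(1/30) = 90.5%.

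| Result | Lower limit, two-sided 95% | Lower limit, one-sided 95% |
|---|---|---|
| 27/30 (bare pass) | 73.5% | 76.1% |
| 29/30 | 82.8% | 85.1% |
| 30/30 | 88.4% | 90.5% |
| 41/45 (bare pass) | 78.8% | 80.8% |
| 44/45 | 88.2% | 89.9% |
| 45/45 | 92.1% | 93.6% |

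The two-sided upper limits for the bare passes are 97.9% (27/30) and 97.5% (41/45). With no failures, the two-sided exact limit first exceeds 90% at n = 36.

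**Step 3: chance of declaring success.** P(X ≥ 27) for X ~ Binomial(30, p), and P(X ≥ 41) for X ~ Binomial(45, p):

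| True rate p | n = 30 | n = 45 |
|---|---|---|
| 80% | 12.3% | 3.8% |
| 85% | 32.2% | 17.5% |
| 90% | 64.7% | 52.7% |
| 95% | 93.9% | 92.7% |

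**Step 4: does the planned table hold the rule's proportion?** Not directly. The total score moves in steps as small as 0.5, so a change of exactly 1 can occur: erythema and dryness each going from 0.5 to 1 gives +1. Reading the rule as an increase of 1 or more, that subject fails it but is not in the SAP 4.4.1.2 count of changes above 1. The denominators also differ: completed subjects in the rule, the Safety population in the analysis. An interval attached to the existing count could therefore describe a different proportion from the one that decides success.

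**The case against.** The absence of inference is declared and consistent across both documents. The study is non-comparative, the sample size rests openly on clinical considerations and a regulatory minimum with no claim of power, and the rule speaks of the subjects observed, so it can be read as a descriptive target. The subject listings and the tabulated counts let a reader compute an interval. All of this is correct, and it is why the point is not an error in the plan. It does not fully answer the point. The non-comparative design explains why the two products are not tested against each other; it does not explain why a single-arm proportion with a success threshold has no stated precision. A descriptive interval adds no test.

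A reader might infer three stronger things that the documents do not support.

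- *That even 30/30 cannot exclude a true rate below 90%.* This depends on a convention that the documents do not set: the exact lower limit is 88.4% two-sided but 90.5% one-sided at 95%. Thirty is also a floor, and 36 or more completers with no failures clear 90% on both.
- *That the rule readily passes poor products.* At a true rate of 80% it fails the product 87.7% of the time with 30 completers (100 − 12.3) and 96.2% with 45 (100 − 3.8). A score increase is also not by itself evidence that the product caused it.
- *That the sample size is wrong.* No power is claimed, so no calculation is contradicted.

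**Conclusion.** The point holds in limited form. The success claim rests on an observed proportion with no planned measure of precision, and at 30 completers that precision is low. A bare pass leaves true rates from 73.5% to 97.9% inside the exact two-sided 95% interval, and even 29/30 has a lower limit below 90% on both conventions. At that size a product with a true rate of 85% would pass about one time in three, and a product exactly at 90% would miss about one time in three (100 − 64.7 = 35.3%). With 45 completers the chances are smaller at 85% (17.5%) and near even at 90%.

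These figures assume independent subjects with a common true rate and the rule's own denominator of completers. The figures for 45 also assume 1:1 allocation and no dropout. The interval reflects sampling variation only; it says nothing about subjects who leave before the final assessment. This is something the sponsor should improve; the plan can be carried out as written.

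**What to change.** In SAP section 4.4.1.2, add a row for each product giving the proportion exactly as the success rule defines it: completed subjects whose total score did not rise by 1 or more, out of all completed subjects. Do not derive it from the count of changes above 1. Beside it give the Clopper-Pearson two-sided 95% CI, with level and sidedness stated and labelled descriptive so that it sits with the no-inference statement. Record the addition in SAP Table 5-1.

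Word the conclusion as *the observed proportion met (or did not meet) the 90% target*, followed by the lower limit. Leave the 90% rule and the sample size unchanged.

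The cost is one row with an interval in an existing table, one entry in Table 5-1 and a sentence of wording, with no new data. The downside is presentational: the reported lower limit will look less favourable than the percentage alone.

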4.4 End of Study Definition

A subject will be considered to have completed the study if they complete all phases of the study, including the last visit or the last scheduled procedure shown in the Schedule of Activities. The end of this study is defined as the date of the last subject's last visit.

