7.2 Lost to Follow up

A subject will be considered lost to follow up if he or she repeatedly fails to return for scheduled visits and is unable to be contacted by the study site.

If a subject fails to return to the site for a required study visit the site must attempt to contact the subject and reschedule the missed visit as soon as possible and counsel the subject on the importance of maintaining the assigned visit schedule and ascertain whether or not the subject wishes to and/or should continue in the study.

Final safety assessments should be carried out wherever possible when the subject returns to the study site, which will include the following:

- Dermatologist assessment of cutaneous irritation
- Ophthalmologist assessment of ocular irritation
- Subject self-assessment questions

Before a subject is deemed lost to follow up, the investigator or designee must make every effort to regain contact with the subject (where possible, 3 telephone calls and, if necessary, a certified letter to the subject's last known mailing address or local equivalent methods). These contact attempts should be documented. If contact is made with the subject, the investigator should inquire about the reason for withdrawal, request that the subject return all products that they had been dispensed and request that the subject return for a final visit, and follow-up with the subject regarding any unresolved adverse events (AEs), and follow-up assessments (dermatologist and ophthalmologist assessments and subject self-assessment questions).

Should the subject continue to be unreachable, he/she will be considered to have withdrawn from the study and lost to follow up.

Lack of completion of all or any of the early termination procedures will not be viewed as protocol deviations so long as the subject's safety was preserved.

If the subject withdraws from the study and also withdraws consent for disclosure of future information, no further evaluations should be performed and no additional data should be collected. The sponsor may retain and continue to use any data collected before such withdrawal of consent.

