12.2.10 Handling of Dropouts and Missing Data

Missing data will not be replaced or imputed. Dropouts will be included in analyses up to the last assessments at the point of discontinuation.

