4.1.1 Subject Disposition

Screen failures are defined as subjects who consent to participate in the clinical study but are not subsequently randomized. A summary will be provided for the number of subjects screened and the number and percentage of screen failures with reasons why subjects are not randomized (PPD [REDACTED]). Percentages for screen failure subjects will be based on number of screened subjects. The number of subjects enrolled for this study will also be presented. A subject who has signed informed consent and is eligible to proceed beyond the screening visit is considered to be enrolled.

Subject disposition will be summarized by the number and percentage of subjects (out of the number of randomised subjects), who complete the study and those who discontinue the study (broken down by reason for discontinuation, if any) (PPD [REDACTED]). The table will also summarize the number and percent of subjects assigned to the Safety Population. The percentages will be based on the total number of subjects randomized.

Subject disposition including the subject status (completed study, Yes/No), demographic data (age, gender and race), screening date, date of study completion or withdrawal, study product start date and time, duration (in days) in the study (defined as [(date of completion or withdrawal – start date of study product) + 1], and primary reason of discontinuation (further details if any) will be listed by product group (PPD [REDACTED]).

Subject disposition information for non-randomized subjects will include subject number, demographic information, screening date and details (if any) regarding the reason for screen failure (PPD [REDACTED]).

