4.1.2 Protocol Deviations

Protocol deviations will be tracked by the study team throughout the conduct of the study. Data will be reviewed prior to unblinding and closure of the database to ensure all important deviations are captured and categorised.

Important deviations of the protocol procedures identified as liable to influence the primary tolerability outcome may include, but will not necessarily be limited to:

- Violation of inclusion or exclusion criteria at screening that may affect primary tolerability.
- Non-compliance with product application.
- Use of prohibited treatment or medication before or during the study which will affect the primary tolerability.
- Violation of the visit window.

Further deviations liable to influence the primary tolerability will be given in the Review Listing Requirement (RLR) document where important deviations will be identified at the BDRM.

The number and percentage of subjects with an important protocol deviation (overall and by type of deviation) will be presented by product group (PPD) and listed in PPD .

All protocol deviations captured on the case report form will be listed in PPD . The listing will present date of deviation, deviation type and deviation description.

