4.4.3 Handling of Missing Values/Censoring/Discontinuations

Missing data will not be replaced or imputed. Subjects who withdraw from the study prematurely will be included in the statistical analyses up to the point of discontinuation.

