4.6.1 Adverse Events and Serious Adverse Events

All AEs will be reviewed by the Clinical Research Scientist or Designee prior to database lock and will be coded to a system organ class (SOC) and preferred term (PT) using the Medical Dictionary for Regulatory Activities (MedDRA). During this review stage, AEs will be further categorized as skin or non-skin.

Treatment emergent adverse events (TEAEs) are defined as new AEs that occur on or after the first product application. Adverse events with an onset date/time prior to the first product application will be considered as non-treatment emergent.

Treatment emergent adverse events will be summarized by the number and percentage of subjects having any AE, an adverse event in each System Organ Class, and each Preferred Term. The following summary tables and listings will be presented by product:

- Table of TEAEs by SOC and PT (PPD [REDACTED]).
- Table of TEAEs by SOC, PT and severity (PPD [REDACTED]).
- Table of TEAEs by skin/non-skin and PT (PPD [REDACTED]).
- Table of treatment emergent treatment-related AEs by SOC and PT (PPD [REDACTED]).
- Table of treatment emergent treatment-related AEs by SOC, PT and severity (PPD [REDACTED]).
- Table of treatment emergent treatment-related AEs by skin/non-skin and PT (PPD [REDACTED]).
- Table of treatment emergent treatment-related serious adverse events (SAEs) by SOC and PT (PPD [REDACTED]) [only produced if there are more than 5 treatment emergent SAEs].
- Table of treatment emergent treatment-related non-serious SAEs by SOC and PT (PPD [REDACTED]) [only produced if there are more than 5 treatment-emergent SAEs].
- Listing of all AEs (PPD [REDACTED] for all randomized subjects; PPD [REDACTED] for non-randomized subjects).

- Listing of deaths (PPD [redacted]).
- Listing of non-fatal SAEs (PPD [redacted]).
- Listing of treatment emergent AEs leading to study or product discontinuation (PPD [redacted]).
- Listing of treatment-emergent AEs classified as skin (PPD [redacted]).

In the event that there is nothing to report, a null listing will be produced.

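### The 90% success figure omits investigational-product subjects who withdraw because of a facial skin reaction, so a supportive percentage should keep them in

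*SAP*

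**What the plan says.** SAP 4.4.1.1 sets the criterion: "This study will be considered a success if at least 90% of completed subjects do not have a significant increase", meaning a one-unit rise in the total of four dermatologist scores, measured as Day 21 minus baseline. Protocol section 3 has the same rule. Protocol 4.4 defines completion: "A subject will be considered to have completed the study if they complete all phases of the study, including the last visit".

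The primary analysis itself is assigned to the Safety population (protocol 12.2.6; SAP 4.1.3 uses that population for tolerability as well as safety). That population takes in anyone who received at least one dose.

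Missing values are not imputed. On early leavers the protocol (12.2.10) says "Dropouts will be included in analyses up to the last assessments at the point of discontinuation" and the SAP (4.4.3) says "Subjects who withdraw from the study prematurely will be included in the statistical analyses up to the point of discontinuation". Protocol 7.2 adds, for subjects who missed a visit, "Final safety assessments should be carried out wherever possible when the subject returns to the study site". Protocol 5.8 schedules only one dermatologist assessment after baseline, at the end of the use period.

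Withdrawals are reported elsewhere. SAP 4.1.1 tabulates "those who discontinue the study (broken down by reason for discontinuation, if any", and SAP 4.6.1 includes a "Listing of treatment emergent AEs leading to study or product discontinuation". However, protocol 5.8, 8.2.1 and 9.2.1 say that a skin response the grading scale can describe is not an adverse event unless the dermatologist finds it unusual.

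**The concern.** This is a tolerance study, and a reaction bad enough to end participation is direct evidence against tolerance. Restricting the success percentage to completers removes exactly those subjects, so the omission is related to the outcome and tends to push the figure up. Success could be declared at 90% or more after women who did not tolerate the serum had been set aside. A reader would have to assemble the disposition table and the adverse event listings to notice, and a graded reaction that was never entered as an adverse event would be missing from the second of these.

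**Working it through.** **Inputs.** The threshold is 90% of completers (SAP 4.4.1.1). The plan is 90 randomized and at least 30 completers per arm (SAP 1.4). The allocation ratio is not stated; equal allocation is assumed, giving 90/2 = 45 per arm. The plan therefore has room for 45 − 30 = 15 non-completers per arm (33.3%). The documents give no rate of reactions, of withdrawals for reactions, or of Day 21 score failures. The sample size rests on clinical considerations and a regulatory minimum of 30, so there is no formula-based figure to reproduce.

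**Where a reaction leaver falls.** She is not a completer (protocol 4.4), so she is outside the success percentage. She is in the Safety population (protocol 12.2.1). With no imputation, she contributes a change score only if she returns for a final assessment, and no rule says such a score enters the 90% figure.

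**Step 1: at the planned minimum of 30 completers.** Let s be the completers who meet the criterion and k the reaction leavers. The written figure is s/30; the supportive figure is s/(30 + k).

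| s | k = 0 | k = 1 | k = 2 | k = 3 | k = 4 |
|---|---|---|---|---|---|
| 27 | 90.0% | 87.1% | 84.4% | 81.8% | 79.4% |
| 28 | 93.3% | 90.3% | 87.5% | 84.8% | 82.4% |
| 29 | 96.7% | 93.5% | 90.6% | 87.9% | 85.3% |
| 30 | 100% | 96.8% | 93.8% | 90.9% | 88.2% |

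**Step 2: starting from 100% of N completers, with N + k ≤ 45.** The smallest k with N/(N + k) < 0.90 is:
- N = 30 to 35: k = 4 (30/34 = 88.2%, 35/39 = 89.7%).
- N = 36 to 40: k = 5 (36/41 = 87.8%, 40/45 = 88.9%).
- N = 41 or more: no k is large enough, since 41/45 = 91.1%.

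**Step 3: chance of reaching 90%, under assumed rates.** Take 45 subjects. Each leaves because of a reaction with probability l. Each who stays is a score failure with probability f. There are no other dropouts. The two probabilities are P(s/(45 − L) ≥ 0.90), the written rule with L leavers, and P(s/45 ≥ 0.90), with leavers kept as failures.

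| f | l | Written rule | Leavers as failures |
|---|---|---|---|
| 5% | 0% | 92.7% | 92.7% |
| 5% | 2% | 93.2% | 80.3% |
| 5% | 5% | 93.7% | 55.0% |
| 5% | 10% | 92.6% | 19.9% |
| 2% | 1% | 99.8% | 98.9% |
| 2% | 2% | 99.8% | 96.8% |
| 1% | 1% | 99.99% | 99.8% |

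At f = 5% the written rule barely moves as reaction leaving rises from 0% to 10%. At rates of 1% to 2% the two figures nearly agree.

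**The case against.** The criterion is prespecified and openly worded, there is no formal inference (SAP 4.4.1.2), and withdrawals are reported by reason. All of that is true, and it limits the seriousness of the point. But the plan has chosen a pass/fail threshold, and none of the other outputs feeds into it.

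The effect depends on assumed rates. This also stands. With a 5% score-failure rate, adding 5% to 10% reaction leavers makes the combined failure rate 9.75% to 14.5%, so a large fall is built in. With rare reactions the gap is about three percentage points or less, and with none it is zero.

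Naming the Safety population might seem to solve the problem already. It does not: the success sentence uses completers, and a leaver without a final score would not count as a failure under either denominator.

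Two stronger readings are tempting. One is that the plan conceals these withdrawals. The documents do not support this: disposition by reason, adverse events leading to discontinuation, and any early final assessment are all provided for.

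The other is that a reaction treated and settled by Day 21 is wrongly scored as a success. It is true that such a subject meets the criterion, but the stated endpoint is status after 21 days, and a treated subject still a unit worse is meant to fail. Protocol 6.8 allows treatment only for adverse events (contraceptives apart), so a treated reaction should either be tabulated as an adverse event or be reviewable under SAP 4.1.2 as "Use of prohibited treatment or medication before or during the study which will affect the primary tolerability". Calling it a failure would create a different and stricter endpoint, which the documents do not require.

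**Conclusion.** The point holds for withdrawals. The success percentage excludes investigational-product subjects who leave because of a facial skin reaction, and the exclusion tends to favour success. How much it matters cannot be known in advance. One leaver is enough to reverse 27/30; from a perfect completer result it takes four or five, and with 41 or more completers that reversal cannot occur. These limits assume 45 per arm, and the probabilities in step 3 also rest on assumed event rates. The documents do not show that the result will be biased, only that the criterion cannot register this form of intolerance. The change is worth making before unblinding, with medium confidence that it will affect the conclusion enough to matter.

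**What to change.** In SAP 4.4.1, keep the completer percentage and report beside it a supportive percentage for the investigational arm. Its denominator is the completers plus every subject who applied the product at least once and discontinued because of a new or worsened facial skin reaction after first application. Those added subjects count as not meeting the criterion. State in the conclusion whether 90% is met on both figures.

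Identify these subjects at the blinded data review from the primary reason for withdrawal (protocol 8.4) and any adverse event record. Count them by default, and do not filter on the investigator's causality rating. Protocol 10.5.2 requires causality only for adverse events, so it will be missing for graded reactions not recorded as such, and protocol 6.5 does not clearly blind the investigator who assigns it.

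Report reactions treated and settled by Day 21 as a separate count beside the two percentages, using adverse event records and the medication indication that protocol 6.8 already collects. Scoring them as failures is an optional endpoint choice for the sponsor.

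The cost is a short SAP addition, the extra output, some blinded judgement where the withdrawal reason is vague, and a supportive figure that may look less favourable. Protocol section 3 needs amending only if the sponsor makes the second percentage a condition of success.
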